#### **4.3. Exclusion criteria**

- Patients with large centrally located pulmonary lesions adjacent to or invading large blood vessels.
- Hemoptysis more than  $\frac{1}{2}$  teaspoon (approximately 2-3 mL) of red blood per day.
- Patients who still have  $\geq$  grade 2 toxicities from prior therapies.
- Concurrent unstable or uncontrolled medical conditions with either of the followings:
  - Active systemic infections;
  - Poorly controlled hypertension (systolic blood pressure  $\geq$  160 mmHg or diastolic blood pressure  $\geq$ 100 mmHg), or poor compliance with anti-hypertensive agents;
  - Clinically significant arrhythmia, unstable angina pectoris, congestive heart failure (class III or IV of New York Heart Association [NYHA]) or acute myocardial infarction within 6 months;
  - Uncontrolled diabetes or poor compliance with hypoglycemics;
  - The presence of chronically unhealed wound or ulcers
  - Other chronic diseases, which, in the opinion of the investigator, could compromise safety of the patient or the integrity of study.
- Newly-diagnosed or symptomatic brain metastases (patients with a history of brain metastases must have received definitive surgery or radiotherapy, be clinically stable, and not taking steroids for brain edema). Anticonvulsants are allowed.
- Any concurrent malignancy other than basal cell carcinoma or carcinoma in situ of the cervix. (Patients with a previous malignancy but without evidence of disease for  $\geq$  3 years are allowed to participate).
- Pregnancy (confirmed by serum beta human chorionic gonadotropin [ $\beta$ HCG]) or breast-feeding (for female patients only).
- A known history or clinical evidence of a deep vein or arterial thrombosis, or pulmonary embolism within 6 months of first infusion of HLX06.
- Less than six weeks from last infusion of ramucirumab, or any other anti-VEGF monoclonal antibody therapy (Last treatment with other monoclonal antibodies targeting proteins other than anti-angiogenic factors is permitted if  $\geq$  4 weeks prior to the first infusion of HLX06).

- Proteinuria  $\geq 2+$  in routine urinalysis (patients with a protein value of  $\leq 500$  mg confirmed by a 24-hour urine collection are eligible).
- Known history of human immunodeficiency virus infection (HIV).
- The patient is the investigator, sub-investigator or any one directly involved in the conduct of the study.

#### **4.4. Randomization and blinding**

- Blinding is not applicable as this is an open-label study.
- The patients of the study are not randomized.

The study site will contact the Sponsor or its designee for treatment assignment once a patient is determined to be eligible for enrollment. Patients who meet all the eligibility criteria will be assigned a number and the dose level for the first infusion as determined by the Sponsor or its designee. Once assigned, numbers for any screening failures, non-treated, non-evaluable, or discontinued subjects will not be re-used.

## **5. STUDY DRUG AND ITS PREPARATION**

All protocol-specified investigational and non-investigational products are considered study drugs.

### **5.1. Investigational product (IP) and non-investigational product**

An investigational product, also known as investigational medicinal product in some regions, is defined as follows: A test article or pharmaceutical form of an active ingredient or placebo that is tested or used as a reference in a clinical trial, including a product with a marketing authorization when used or assembled (formulated or packaged) in a way different from the approved form, used for an unapproved indication, or used to gain further information about an approved use.

The IP is HLX06 in this study.

Other medications used in the study as support or escape medication for preventative, diagnostic, or therapeutic reasons, as components of the standard of care for a given diagnosis, are considered non-investigational products.

In this protocol, non-investigational product(s) is/are: Not applicable for this study.

### **5.2. Description of IP**

HLX06 is recombinant human IgG1 monoclonal antibody directed against human VEGFR2. The study agent will be provided by the Sponsor. The rest of medications are provided by study sites.

### **5.3. Product appearance, storage, stability and formulation**

HLX06 is supplied in a single-use 10 mL vial. Each vial contains 100 mg active drug in 10 mL clear, colorless solution and should be stored at 2-8 °C. The drug is expected to be stable up to two years when stored at 2-8 °C. In addition to the active ingredient, the main ingredients in the solution are sucrose, sodium chloride, sodium citrate, and polysorbate 80. Detailed information on formulation is described in the Investigator's brochure. The product storage manager should ensure that the investigational product is stored in accordance with the environmental conditions (temperature, light, and humidity) as determined by the Sponsor. If concerns

regarding the quality or appearance of the investigational product arise, do not dispense the investigational product and contact the Sponsor immediately.

Investigational product should be stored in a secure area per local regulations. It is the responsibility of the Investigator to ensure that investigational product is only dispensed to study patients. Investigational product must be dispensed only from official study site by authorized personnel according to local regulations.

#### **5.4. Packaging and labeling**

The investigational product will be packaged and labeled per current good manufacturing practices (GMP).

#### **5.5. Ordering investigational products**

Clinical supplies may be requested by completing a Request Form and faxing it or e-mail it to the Drug Supply Coordinator of the Sponsor or its designee.

#### **5.6. Preparation of investigational product and administration**

HLX06 is intended for **intravenous** injection only with final concentration no more than 10 mg/mL

To minimize the error in the adjustment of infusion rate, HLX06 is constituted to the final volume of **200 mL** with normal saline and infused intravenously in **two hours**, regardless of the assigned dose level. Diluted HLX06, if not used in 4 hours, should be stored at 2-8 °C and be used in 24 hours.

The following procedure is required to prepare the HLX06 solution.

Confirm the dose needed to be infused and calculate the volume needed. Draw up the volume of a vial of HLX06 using a sterile syringe.

Fill HLX06 in a sterile evacuated container or bag such as glass containers, polyolefin bags (ethylene vinyl acetate bags, DEHP plasticized PVC bags, or PVC bags).

Repeat the procedure until the calculated volume has been put in to the container. Use a new needle for each vial.

Dilute the drawn HLX06 with sterile 0.9% saline solution to make the final volume of 200 mL.

Administer through a low protein binding 0.22-micrometer in-line filter (placed as proximal to the patient as practical). Affix the infusion line and prime it with diluted HLX06 before starting the infusion. **Set the infusion rate to 100 mL per hour.**

At the end of infusion period, flush the line with sufficient amount of normal saline.

#### **5.6.1. Three DON'Ts in preparation of HLX06 for infusion**

- DON'T enter the vial more than once.
- DON'T piggyback to the patient's other infusion line. HLX06 should be infused using a separate infusion line.
- DON'T administer HLX06 as an intravenous push or bolus injection.

#### **5.7. Drug accountability**

HLX06 must be kept in an appropriate, secure locked area and stored in accordance with the conditions specified on the labels.

The Investigator or designated study person must maintain an accurate record of dispensing the investigational product in a Drug Accountability Log, a copy of which must be given to the Sponsor at the end of the study. The Drug Accountability Log will record the investigational products received, dosages prepared, time prepared, doses dispensed, and doses and/or vials destroyed. The Drug Accountability Log will be reviewed by the field monitor during site visits and at the completion of the study.

#### **5.8. Disposal of investigational product**

If investigational products are to be destroyed on site, it is the investigator's responsibility to ensure that arrangements have been made for the disposal, procedures for proper disposal have been established according to applicable regulations, guidelines and institutional procedures, and appropriate records of the disposal have been documented. Unused HLX06 should be returned to the Sponsor after the study. Used vials can be disposed at the study site following institutional guidelines for investigational product. Vials without proper labeling or suspected of contamination should not be used and returned to the Sponsor.

## **6. ASSESSMENT OF SAFETY AND MANAGEMENT OF TOXICITIES**

### **6.1. Dose limiting toxicities (DLTs)**

DLTs are side effects of a drug or other treatment that are serious enough to prevent an increase in dose or level of that treatment in a clinical study. We use Common Toxicity Criteria for Adverse Events (CTCAE) 4.0 for grading of toxicities in this study.

The definition of DLTs in this study is the toxicities during the first cycle of treatment:

A DLT will be considered to be IP-related unless there is a clear, well-documented, alternative explanation for the toxicity. Delayed DLTs are adverse events that meet the criteria of DLTs that occur after the first cycle of treatment. Delayed DLTs need to be evaluated on a case-by-case basis to make sure that there is no cumulative damage to vital organ function.

Delayed DLTs will also be considered to estimate the MTD for HLX06 in this study.

All adverse events that meet DLT or delayed DLT criteria, as well as any Grade 3 or 4 infusion reactions no matter whether the event is a DLT must be reported to the Sponsor or its designee, within 24 hours.

### **6.2. Stopping rules for clinical deterioration**

Clinical deterioration is defined by the clinical condition of the patient has worsened and, in the Investigator's opinion, is attributable to disease progression. Such deterioration is not likely to be reversed with additional administration of Investigational Product and supportive care. The decision to continue or stop treatment should be discussed with the Medical Monitor and documented in the study records.

Events that suggest clinical deterioration include, but not limited to the following:

- Performance status decrease of at least 2 points from baseline
- Skeletal related events defined by the following
  - Pathologic bone fracture in the region of cancer involvement
  - Cancer related surgery to bone
  - Spinal cord or nerve root compression
- Bladder outlet or urethral obstruction
- Development of new central nervous system metastases

- Patients that develop new CNS metastases in the setting of improving baseline disease may have focal radiation, resection, or other local curative procedures performed after consultation with the Medical Monitor.
- If continued study therapy is deemed to offer the patient potential benefit, patients may be allowed to restart study therapy after recovery from symptoms related to the procedure performed (i.e., local edema) and steroid dosing at < 10 mg prednisone/day or equivalent.
- Patients that have locally curative procedures while on study drug and subsequently develop new CNS metastases at a subsequent imaging assessment should discontinue study therapy and enter the follow-up period.
- Or any setting where the initiation of new anti-neoplastic therapy has been deemed beneficial to the patient even in the absence of any such documented clinical events.

### **6.3. Strategies to mitigate the risk of severe adverse events and toxicities**

To mitigate the risk of HLX06 first-in-human use, the interval of first infusion of investigational product between NEW patients in a cohort is **24 hours or longer**.

### **6.4. Management of possible toxicities**

HLX06 has not been used in human beings before. There is no clinical experience to define expected toxicities to humans. Based on its mode of action, the spectrum of toxicities is expected to be similar to what have been described for anti-angiogenesis agents, such as bevacizumab, ramucirumab or other small molecule inhibitors for anti-angiogenesis (e.g. sunitinib, sorafenib). The following are the common or severe toxicities by bevacizumab and ramucirumab and their respective management.

**Allergic reaction/hypersensitivity and infusion-related reactions:** Fever, chills, shakes, itching, rash, hyper- or hypotension, difficulty breathing. It is likely that most infusion-related adverse events will occur within the first 24 hours after beginning the infusion, and may be treated by slowing or interruption of the infusion, or with supportive treatment as indicated. The common agents used to treat hypersensitivity agents are anti-histamine, H2-blockers, corticosteroid. Severe anaphylactic reactions might require epinephrine treatment. Infusion reaction should be graded according to NCI CTCAE criteria. Treatment recommendations are as follows:

- **Grade 1 symptoms:** If the Investigator assesses that it is a mild reaction and infusion interruption is not indicated, the prophylactic pre-medications are recommended: diphenhydramine 30-50 mg (depending on institutional availability or equivalent medications), acetaminophen 325-500 mg PO at least 30 minutes before additional IP infusion.
- **Grade 2 symptoms:** If the Investigator assesses that it is a moderate reaction, requiring therapy or infusion interruption, stop the IP infusion and begin with intravenous infusion of normal saline, and treat the patients with diphenhydramine 30-50 mg (or equivalent medications) intravenously, and dexamethasone 10 mg (or corticosteroids with equivalent potency) intravenously. After the symptoms have subsided, restart the infusion at 50% of original infusion rate. Monitor the patient closely. If the symptoms recur, no further IP infusion at that visit. Prophylactic pre-medications with diphenhydramine, acetaminophen and corticosteroid are indicated for future infusion of IP.
- **Grade  $\geq 3$  symptoms:** It is severe reaction, and recurs, or does not rapidly respond to symptomatic treatment and interruption of infusion, stop the infusion of IP immediately. Consider 0.2 to 1 mg of 1:10,000 solution of epinephrine for subcutaneous administration. Diphenhydramine 30-50 mg intravenous with methylprednisolone 100 mg (or equivalent) intravenously, as needed. Hospitalization might be needed for possible clinical sequelae.

**Hypertension:** Hypertension is among the most common toxicities of anti-angiogenic therapy. The incidence of hypertension could reach 20% by a single anti-angiogenic agent. Initiation of antihypertensive medications should be considered when BP is  $>140/90$ mmHg or if there is an increase in DBP  $\geq 20$ mmHg. If SBP  $>160$ mmHg, DBP  $>100$ mmHg, hypertensive crisis or if antihypertensive interventions do not provide appropriate BP control, the dose level of HLX06 should be decreased or held until antihypertensive therapy is effectively titrated. Although appropriate BP control is essential, excessive lowering of BP may also have detrimental cardiovascular consequences; careful selection of doses and close BP monitoring are crucial to avoid episodes of hypotension. Multiple antihypertensive drugs are being used to treat anti-angiogenic therapy-induced hypertension including calcium channel blockers, inhibitors of the renin-angiotensin system, beta-blockers and diuretics. At this time, however, no clinical evidence favoring one antihypertensive agent over another is available [19].

**Bowel perforation:** Clinical trials have revealed that 1-4% of colorectal cancer patients receiving bevacizumab could develop spontaneous bowel perforation. It could also occur in patients who have no involvement of cancer in the gastrointestinal tract. Several risk factors for bevacizumab-associated bowel perforation have been identified, including a history of peptic ulcer disease, diverticulitis, colitis, intestinal obstruction, tumor necrosis, recent sigmoidoscopy or cumulative dose of bevacizumab, radiotherapy, or emergent surgery while receiving bevacizumab, it is still unclear which patients are specifically at risk for this complication. Gastrointestinal perforation could lead to peritonitis, requiring emergent operative intervention, fistula formation or intra-abdominal abscess[20]. Bowel perforation could be hard to diagnose in patients without symptoms. If the symptoms are present, it usually presents as acute abdomen due to peritoneal contamination, hemoperitoneum, or free intra-abdominal air, or intra-abdominal abscess. The management of bowel perforation depends on the timing of the presentation, the overall condition of the patients and the goals of treatment. Medical treatment is usually ineffective. More likely, patients need to receive surgical intervention. The long half-life of monoclonal antibody increases the risk of unplanned, urgent surgical procedures. For patients who have received HLX06 therapy, surgery within 28 days following their last treatment should be avoided. If surgery is necessary, risk-and-benefit assessment should be conducted by experienced surgeons.

**Severe proteinuria:** This is another common side effects observed in anti-angiogenic therapy. Severe proteinuria including nephritic syndrome may cause significant morbidity with a possible consequence of renal failure and fatality. It is recommended to suspend anti-angiogenic therapy at least temporarily for proteinuria  $\geq 2$  g/24 hours and to discontinue the therapy for nephrotic syndrome. The risks of severe proteinuria include higher dose of therapy, concurrent use of chemotherapy and renal cell carcinoma.[21] There are no evidence-based guidances for the management of anti-angiogenic therapy-induced proteinuria. If proteinuria is  $\geq 2$  g/24 hours during HLX06 therapy, stop the therapy, and the patients might resume the therapy after proteinuria decreases to  $<2$  g/ 24 hours at the next lower dose level, if the benefit of HLX06 is deemed to outweigh the risks, as judged by the Investigator.

**Bleeding:** This is a frequent complication of anti-angiogenic therapy. Two meta-analyses have found that the use of bevacizumab in combination with chemotherapy for the treatment of various tumor types conferred an increased risk of severe and fatal bleeding events and treatment-related mortality versus chemotherapy alone. Most cases involve low-grade mucocutaneous bleeding that can be managed by local treatment and usually does not interrupt

treatment. Epistaxis is another common bleeding. Studies have shown that the rates of grade 1-2 epistaxis range from 5-26%. Mild-to-moderate Epistaxis is usually managed conservatively. However, in severe cases, operative hemostatic intervention might be indicated. In such cases, otolaryngologists with experience in managing drug-induced bleeding should be consulted. Intracranial hemorrhages are associated with bevacizumab use especially in patients with glioblastoma multiforme[22]. The highest incidence of high-grade bleeding is associated with non-small cell lung cancer, especially with squamous cell histology. This risk is particularly high in patients with persistent hemoptysis before study. This led the exclusion of patients with this histology and patients with hemoptysis in most of subsequent clinical studies for lung cancer. Well patient selection might be the best strategy to prevent this complication. Once bleeding is identified, appropriate management is based on the site and the degree of bleeding. In sites where bleeding cannot be controlled by compression, or when the degree of bleeding is severe, surgical intervention might be needed for better control.

**Poor wound healing and fistula formation:** Anti-angiogenic therapy compromises neovasculization, and affects wound healing. Pooled analysis from bevacizumab studies found 13% wound-healing complication. When surgery was done within 2 weeks after last bevacizumab dose, the risk of poor healing is higher. So far, specific recommendation for the management of poor wound healing has not been established. General recommendation is that surgery should be avoided within 60 days of bevacizumab when chemotherapy is used together or within 28 days when monotherapy is used.[23]

**Thromboembolism:** Anti-angiogenic therapy not only increases the risk of bleeding, it also increases the risk of thromboembolism[22]. The risk factors associated with thromboembolism is age older than 65, advanced cancer, and the location of tumors. The incidence of thromboembolism was highest in patients with colorectal cancer. However, there is not standard recommendation for prevention of thromboembolism by prophylactic use of anti-coagulants. The Investigator should remain high alert on the emergence of thromboembolism and manage the complication accordingly.

**Tumor lysis syndrome:** Tumor lysis syndrome has been described in patients receiving chemotherapy/ bevacizumab or sunitinib[24]. This may result in asymptomatic laboratory abnormalities to clinical changes secondary to electrolyte disturbances, including cardiac arrhythmias, neuromuscular irritability, tetany, seizures, and mental status changes (hypocalcemia), acute renal failure (hyperuricemia and hyperphosphatemia), and metabolic

acidosis (acute renal failure and lactic acidosis). The management of tumor lysis syndrome induced by anti-angiogenic therapy is similar to that by other anti-cancer agents. In general, resumption of anti-cancer therapy is judged by the patient's condition and the decision of Investigator.

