#### **7.2.2.4. Management for the infusion-related reactions**

For patients who experience first infusion reactions, please refer to Section 6.4 for the procedure and management.

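### The epinephrine advice for grade 3 or higher infusion reactions works out to 2-10 mL subcutaneously, which is doubtful enough that dose, concentration, volume and route should be confirmed or replaced

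*Combined protocol and SAP*

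**What the plan says.** Section 6.4 sets out graded recommendations for allergic and infusion-related reactions. Its introduction mentions epinephrine only in general terms: "Severe anaphylactic reactions might require epinephrine treatment". The entry for grade 3 or higher covers a severe reaction that recurs or "does not rapidly respond to symptomatic treatment and interruption of infusion, stop the infusion of IP immediately". It then gives the only epinephrine dose in the document: "Consider 0.2 to 1 mg of 1:10,000 solution of epinephrine for subcutaneous administration". The same entry adds intravenous diphenhydramine and methylprednisolone as needed, and notes that hospitalization might follow.

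Section 7.2.2.4 makes this the working text for sites: "For patients who experience first infusion reactions, please refer to Section 6.4 for the procedure and management". No other section gives an epinephrine dose, dilution, volume or route.

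**The concern.** The sentence fixes three things at once: an amount in milligrams, a dilution and a route. Together they determine a volume that the protocol never states. In the infusion-reaction text epinephrine is the only drug given with a dilution. Diphenhydramine, dexamethasone and methylprednisolone are given in milligrams alone, so only the epinephrine line commits a site to a particular volume.

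That volume is large for an injection under the skin during an emergency, and it would be ten times smaller at a 1:1,000 dilution. This raises the question whether the dilution, the unit or the route was written as intended. A member of staff who notices the volume mid-reaction cannot tell from the protocol which element to trust.

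The situation is foreseeable. HLX06 has not been given to humans before. Section 7.2.2.2 does not require prophylaxis before the first infusion. Section 8.2 notes that anti-drug antibodies may predispose patients to infusion reactions on retreatment. Section 10.8 requires rapid notification of grade 3 or 4 infusion reactions.

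**Working it through.** **Inputs, all from the grade 3 or higher entry in Section 6.4**
- Dose: 0.2 to 1 mg.
- Dilution: "1:10,000 solution of epinephrine".
- Route: "for subcutaneous administration".

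The protocol states no volume, so there is no printed result to reproduce. The check is a unit conversion.

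**Step 1: concentration.** A 1:10,000 weight-in-volume ratio is 1 g in 10,000 mL, so 1,000 mg / 10,000 mL = 0.1 mg/mL.

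**Step 2: volume = dose / concentration.**
- Low end: 0.2 mg / 0.1 mg/mL = 2 mL.
- High end: 1 mg / 0.1 mg/mL = 10 mL.

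**Step 3: what each possible correction would mean.**

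| Element changed | Dose | Volume |
|---|---|---|
| None (as written) | 0.2-1 mg | 2-10 mL subcutaneously |
| Dilution becomes 1:1,000 (1 mg/mL) | 0.2-1 mg | 0.2-1 mL |
| Unit becomes mL of 1:10,000 | 0.02-0.1 mg (0.2 x 0.1 to 1 x 0.1) | 0.2-1 mL |
| Route becomes something other than subcutaneous | 0.2-1 mg | 2-10 mL by that route |

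The second and third rows give the same volume but differ tenfold in drug: 0.2 / 0.02 = 10 and 1 / 0.1 = 10. A site that guesses at the intended correction could therefore be wrong by that factor. None of the alternative rows has direct support in the text. They show only why the sentence needs confirming at source.

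**Step 4: dependence on an assumed volume limit.** The documents give no maximum for a single subcutaneous injection. Writing V for an assumed limit in mL, the 1 mg dose needs 10/V injections, rounded up: ten at V = 1, five at V = 2, two at V = 5 and one at V = 10. The 0.2 mg dose needs two at V = 1 and one at V = 2 or more. How awkward the instruction is therefore depends on a figure from outside the documents. The 2-10 mL itself does not.

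**The case against.** The strongest reply is that nothing in the protocol contradicts the sentence. Dose, dilution and route are compatible with each other, and no section gives a conflicting concentration, volume or limit. Calling 2-10 mL excessive needs a premise that the documents do not supply. The sentence does not require a single injection, and the low end is 2 mL. The amount of drug is clear as written, so no wrong dose is ordered. The language is advisory: the entries are headed as recommendations, epinephrine might be required, and the investigator is asked to consider it. Section 13.1 also says that approval requirements must not hold back immediate action to protect patients.

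Most of this stands, and it rules out several stronger readings:
- A reader might infer that the dilution is a proven misprint for 1:1,000. The documents do not show which element is wrong, or exclude that the text is as intended.
- A reader might infer that the protocol orders an overdose or underdose. It does not; as written, the dose is 0.2-1 mg.
- A reader might infer that most of the dose range cannot be given. That needs both a volume limit and a single-injection rule, and the protocol sets neither.
- A reader might infer that sites are obliged to inject a large volume. The wording leaves them free to follow their own procedure.

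The objection does not dispose of the volume. It follows from the sentence alone, the protocol neither states it nor says how to give it, and sites are directed to this text. Freedom to depart from a doubtful emergency instruction is not a reason to leave it in print.

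**Conclusion.** The point holds as a defect in safety wording that should be corrected. The certain part is the conversion: 0.2-1 mg of a 1:10,000 solution is 2-10 mL, and the protocol directs it subcutaneously without mentioning volume or divided dosing. The judgement is that this combination is doubtful enough, with the same dose occupying 0.2-1 mL at 1:1,000, not to stand unconfirmed as guidance for a severe reaction in a first-in-human trial.

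That judgement assumes that up to 10 mL under the skin is awkward in an emergency. This is a clinical premise that the documents neither state nor refute. Exposure is limited because the advice is discretionary and applies only to severe reactions that recur or do not respond quickly. The Bayesian optimal interval rules, the dose-limiting toxicity definitions, the maximum tolerated dose estimate and the planned analyses are not touched.

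**What to change.** Either of two changes to the epinephrine sentence in Section 6.4 would do:
1. Replace it with an instruction to give epinephrine according to the site's approved anaphylaxis procedure.
2. Have the sponsor's medical and pharmacy leads confirm the intended treatment and print one consistent set: dose in mg, concentration in mg/mL, volume in mL, and route.

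The first is simpler and does not depend on establishing what was meant. In either case, notify sites by memo. The cross-reference in Section 7.2.2.4 can stay as it is.

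The cost is a one-sentence amendment and the memo. Under Section 13.1, an amendment that significantly affects patient safety also needs approval from the IRB/IEC of every center and from the local regulatory authority, so the sponsor may have to allow for that. Design, sample size and analysis do not change.
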